8.3.1 Confirming Progression

Unlike RECIST 1.1, iRECIST requires the confirmation of progression and uses the terms iUPD (unconfirmed progression) and iCPD (confirmed progression). Confirmatory scans should be performed at least 4 weeks, but no longer than 8 weeks after iUPD.

iCPD is confirmed if further progression, compared to the last assessment, is seen as evidenced by one or more of the following:

- Continued progression where RECIST 1.1 definitions of progression had been met (from nadir) in target, non-target disease or new lesions (from uPD):
 - Progression in target disease worsens with an increase of at least 5 mm in the absolute value of the sum;
 - Continued unequivocal progression in non-target disease with an increase in tumour burden;
 - Increase in size of previously identified new lesion(s) (an increase of at least 5 mm in the absolute value of the sum of those considered to be target new lesions);
- RECIST 1.1 criteria are met where progression was not previously identified, including the appearance of additional new lesions.

If iUPD is not confirmed at the next assessment, then the appropriate response will be assigned (iUPD is the criteria are still met, but no worsening, or iSD, iPR or iCR if those criteria are met compared to baseline). As can be seen in Table 3, the prior documentation of iUPD does not preclude assigning iCR, iPR, or iSD in subsequent time-point assessments or as best overall response (BOR) providing that iCPD is not documented.

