8.3.2 New Lesions

New lesions should be assessed and measured as they appear using RECIST 1.1 criteria (maximum of 5 lesions, no more than 2 per site, at least 10 mm in long axis (or 15 mm in short axis for nodal lesions), and recorded as New Lesions-Target (NLT) and New Lesion-Non-Target (NLNT) to allow clear differentiation from baseline target and non-target lesions.

New lesions may meet the criteria of NLT or NLNT to drive iUPD (or iCPD). However, the measurements of target lesions should NOT be included in the sum of measures of original target lesions identified at baseline. Rather, these measurements will be collected on a separate table in the case record form. These data will enable the development and testing of alternate response criteria, or further modifications of RECIST.

PD is confirmed in the New Lesion category if the next imaging assessment, conducted at least 4 weeks (but not more than 8 weeks) after iUPD confirms further progression from iUPD with either an increase of at least 5 mm in the absolute value of the sum of NLT OR an increase (but not necessarily unequivocal increase) in the size of NLNT lesions OR the appearance of additional new lesions.

Table 2: Time-point (TP) iResponse

Target Lesions*	Non-Target Lesions*	New Lesions*	Time Point Response	
			No prior iUPD**	Prior iUPD**
CR / iCR	CR	No	CR	iCR
CR/iCR	Non-CR/Non-PD Non-iCR/Non-iUPD	No	PR	iPR
PR/iPR	Non-CR/Non-PD Non-iCR/Non-iUPD	No	PR	iPR
SD/iSD	Non-CR/Non-PD Non-iCR/Non-iUPD	No	SD	iSD
iUPD with no change OR decrease from last TP	iUPD with no change OR decrease from last TP	Yes	NA	The appearance NLs confirms PD if Additional NLs or iUPD in last TP based on NLs and increase in size (≥ 5 mm for NLT or any increase for NLNT) If no change in NLs from last TP, remains iUPD
PD	Non-CR/Non-PD Non-iCR/Non-iUPD	No	iUPD	Remains iUPD unless iCPD confirmed based on further increase in sum of at least 5 mm, otherwise remains iUPD
PD	PD	No	iUPD	iCPD if further increase in previously identified*** T lesion iUPD ≥ 5 mm and / or NT lesion iUPD
PD	PD	Yes	iUPD	iCPD if further increase in previously identified T lesion iUPD ≥ 5 mm and / or NT lesion iUPD and / or size or number of new lesion
Non-iUPD	Non-iUPD	Yes	iUPD	iCPD if increase in size of previously identified new lesions or increased number of new lesion

* Using RECIST 1.1 principles. If no pseudoprogression occurs, RECIST 1.1 and iRECIST categories for CR, PR and SD would be the same.
 ** In any category.

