 *** Previously identified in assessment immediately prior to this time-point (TP)
 NA = not applicable.

Table 3: iRECIST Best Overall Response (iBOR)

All patients will have their iBOR from the start of study treatment until the end of treatment classified as outlined below.

TPR1	TPR2	TPR3	TPR4	TPR5	iBOR	
CR	CR, PR, iUPD, NE	CR/iCR, iUPD, iCPD, NE	PR/iPR, iUPD, NE	iUPD	iCPD	iCR
iUPD	PR, SD, NE	CR		CR, PR, SD, iUPD, NE	SD, iUPD, iCPD, NE	iCR
iUPD	PR	PR, SD, iUPD, NE		PR, SD, iUPD, NE, cPD	PR, SD, iUPD, NE, iCPD	iPR
iUPD	SD, NE	PR		PR, SD, iUPD, NE	PR, SD, iUPD, iCPD, NE	iPR
iUPD	SD	SD, iUPD, NE		SD, iUPD, iCPD, NE	SD, iUPD, iCPD, NE	iSD
iUPD	iUPD	Anything		Anything	Anything	iCPD
iUPD	iUPD	iCPD		Anything	Anything	iCPD
iUPD	NE	NE		NE	NE	iUPD
1. Table assumes a randomized study where confirmation of CR or PR is not required. 2. NE = not evaluable that cycle. 3. Designation "I" for BOR can be used to indicate prior uPD to aid in data interpretation. 4. For patients with non-target disease only at baseline, only CR or non-CR/non-PD can be assigned at each TPR but is not shown in the table for ease of presentation.						

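### After an unconfirmed progression resolves, 8.3.1 and Table 2 can score the next progression as confirmed (iCPD) on a single scan, in conflict with the confirmation requirement and Table 3

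*Combined protocol and SAP*

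**What the plan says.** Section 8.3.1 opens with the principle: "Unlike RECIST 1.1, iRECIST requires the confirmation of progression and uses the terms iUPD (unconfirmed progression) and iCPD (confirmed progression". It sets the timing, "Confirmatory scans should be performed at least 4 weeks, but no longer than 8 weeks after iUPD", and the test, "iCPD is confirmed if further progression, compared to the last assessment, is seen as evidenced by one or more of the following". The last item on that list is the one at issue: "RECIST 1.1 criteria are met where progression was not previously identified, including the appearance of additional new lesions".

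For an iUPD that does not hold up, 8.3.1 says "If iUPD is not confirmed at the next assessment, then the appropriate response will be assigned". The options are iUPD again, iSD, iPR or iCR. It does not say how a progression after that is to be scored.

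Table 2 in 8.3.2 has two result columns, without and with a prior iUPD. A note says that the prior iUPD may be in any category. It sets no time limit and does not exclude an iUPD that has resolved. Two cells of the prior-iUPD column matter here:

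- Target progression alone: "Remains iUPD unless iCPD confirmed based on further increase in sum of at least 5 mm, otherwise remains iUPD".
- New lesion alone: "iCPD if increase in size of previously identified new lesions or increased number of new lesion".

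A three-star footnote, "Previously identified in assessment immediately prior to this time-point (TP", would limit the look-back, but its marker stands only on the row with target and non-target progression and no new lesion.

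**The concern.** iRECIST asks for confirmation because one increase may be pseudoprogression. A patient whose iUPD has resolved has already had one increase that was not confirmed. If the next increase is read in the prior-iUPD column, that patient loses the confirmation step.

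The label has consequences. Section 8.3.1 allows a later iCR or iPR only if iCPD has not been documented. Section 10.1 treats clinically stable patients with iUPD differently from patients with iCPD. Under 5.0 and 10.4, patients with confirmed progression move to follow-up for survival and other treatment, apart from ongoing toxicity, so a later response might not be imaged. Two careful assessors could score the same patient differently on the criteria that define the primary endpoint in 13.2.

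**Working it through.** **Design figures.** No number in the plan depends on this rule. The only related figures are those of the two-stage design in 13.3 (0/12 stops, at least 4/37 succeeds), and they reproduce. P(success | p) = Σ over x = 1 to 12 of C(12,x) p^x (1−p)^(12−x) × P(Bin(25,p) ≥ 4−x). This gives 0.0935 at p = 0.05 and 0.9024 at p = 0.20, within the stated error rates of 0.1. The finding does not change them.

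**Inputs for the trace.** Under 8.2.5, target PD is at least 20% and at least 5 mm above the smallest sum on study. Table 2 (target-only row) asks for a further increase of at least 5 mm, and 8.3.1 sets the last assessment as comparator. Scans are every 12 weeks, with a repeat 4 to 8 weeks after iUPD (5.0). The sums in mm are illustrative and not from the documents.

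| Scan | Record A | Record B |
|---|---|---|
| Baseline | 50 | 50 |
| Week 12 | 62: +12 mm, 12/50 = 24%, iUPD | 62: iUPD |
| Week 18 | 51: +1 mm, 2%, iSD | 58: +8 mm, 16%, iSD |
| Week 24, against nadir 50 | 61: +11 mm, 22%, PD | 62: +12 mm, 24%, PD |
| Week 24, against last scan | 61 − 51 = +10 mm | 62 − 58 = +4 mm |
| Literal Table 2 result | iCPD on one scan | stays iUPD |

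In Record A the week 24 sum is 1 mm below the week 12 sum that was not confirmed (61 − 62 = −1).

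**When the literal rule bites.** Let N be the nadir and L the last sum. Single-scan iCPD needs a sum of at least 1.2N, at least N + 5 and at least L + 5. If L = N, the third condition repeats the second, so every target PD qualifies. With N = 50, PD starts at 60 mm (1.2 × 50). At L = 51 the third threshold is 56, so every PD qualifies. At L = 58 it is 63, so a sum of 60 to 62 mm is PD but remains iUPD.

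**New lesions.** After an iUPD in target lesions has resolved, a first new lesion raises the number of new lesions from 0 to 1. It meets the new-lesion cell of Table 2 and the last bullet of 8.3.1 on its first appearance.

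**Passages that point the other way.**

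- 8.3.1 requires confirmation, by a scan 4 to 8 weeks after iUPD.
- The new-lesion text of 8.3.2 ties confirmation to the imaging assessment that follows the iUPD, in the same window.
- Table 3 has four rows in which iUPD is followed by SD, PR or CR. In each, the time point directly after the response that defines the row lists iUPD but not iCPD. For iUPD then SD, the third time point allows SD, iUPD or not evaluable. Record A is that sequence, so Table 3 gives iUPD where Table 2 gives iCPD.

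**How many patients could be exposed.** The documents give no rate of resolved iUPD. If 5% to 15% is assumed, 12 × 0.05 = 0.6 to 12 × 0.15 = 1.8 patients per arm in stage 1, and 37 × 0.05 = 1.9 to 37 × 0.15 = 5.6 per full arm, would have one. These are upper limits on the patients at risk of mis-scoring, because each also needs a later progression of the kind described.

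**The case against.** The strongest reply is that the protocol already implies a reset. Table 3, to which 8.3.1 itself refers, behaves as if there were one. The wording of the target cell (remaining iUPD, a further increase) presupposes an iUPD that is still open. Record A also fits neither 8.3.1 bullet well: nothing is continuing after iSD, and target progression had been identified before. Finally, 8.3 presents itself as a summary of the key differences from a cited guideline, which may settle the matter.

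Part of this stands. The target example rests on Table 2 alone; only the new-lesion example rests on both 8.3.1 and Table 2. Table 3 shows the likely intention. But it lists options rather than rules, and one time point later it allows iCPD without requiring an iUPD in between. The comparison with the last assessment does not help, because after resolution the last sum is the low one and 5 mm is easier to reach. What a cited guideline may say does not reconcile two tables in the protocol.

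A reader might infer that any progression after a resolved iUPD is scored iCPD at once. Record B shows that this is not so. A reader might also infer a material bias in the primary response rate. The documents do not support that either: Table 3 keeps a response reached before iCPD, and Section 13 names no analysis based on iCPD.

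**Conclusion.** The point holds as an internal inconsistency. Literal scoring under 8.3.1 and Table 2 can give iCPD on one scan after a resolved iUPD, for a first-ever new lesion or for a target PD at least 5 mm above the last assessment. The confirmation requirement, the new-lesion text of 8.3.2 and Table 3 indicate a fresh iUPD instead.

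The effect is mainly on the iCPD call and its date, and on which part of 10.1 applies to a clinically stable patient. The effect on the iRECIST response rate is small, confined to patients with no earlier response whose first response would come after a premature iCPD. Its frequency cannot be derived from the documents. The exposure range above rests on an assumed rate and does not count mis-scored patients. Sample size, alpha and power are unaffected. The correction is worth making because it is cheap and the criteria concerned define the primary endpoint.

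**What to change.** Reconcile 8.3.1 and Table 2 with Table 3:

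- Add to 8.3.1: *If iUPD is followed by iSD, iPR or iCR, the next progression in any category is scored as a new iUPD and needs its own confirmation.*
- In Table 2, extend the three-star qualifier (identified at the assessment immediately before) to the prior-iUPD cells of the PD and new-lesion rows only.
- Leave the two-star note and the iCR, iPR and iSD rows as they are. Narrowing that note for the whole table would turn iPR, iSD or iCR after a resolved iUPD into PR, SD or CR and lose the prefix that marks a prior iUPD.
- Check that 10.1 is consistent with the reconciled definition of iCPD. What 10.1 should require clinically is outside this point.

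The cost is protocol wording and the derivation logic for iRECIST time-point responses. Some iCPD calls will come one scan later. In Record A the confirming scan would fall at week 28 to 32 (24 + 4 to 24 + 8). That repeat scan is already required after iUPD, so no new assessment is added.

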2. Patients will be monitored before, during and after the first cycle infusion of tremelimumab and durvalumab with assessment of vital signs to be collected \leq 30 minutes prior to start of infusion then every 30 \pm 5 minutes during infusion; a 1-hour observation period is recommended after the tremelimumab. Assessment of vital signs in subsequent cycles is required prior to the start of the infusion, and then as clinically indicated. If no clinically significant infusion reactions are observed during or after the first cycle of tremelimumab+durvalumab therapy, subsequent infusion observation periods can be at the investigator's discretion.
3. Pre-treatment blood draws and physical exams may be done one working day prior to treatment if necessary (e.g. Friday for treatment on Monday, or to accommodate holidays). In order to ensure that nadir counts are not missed, every effort should be made to do interim blood draws within 24 hours of the day specified in the protocol. If a patient shows an AST or ALT $\geq 3 \times$ ULN together with total bilirubin $\geq 2 \times$ ULN, refer to Appendix II for further instructions on cases of increases in liver biochemistry and evaluation of Hy's Law. These cases should be reported as SAEs if, after evaluation, they meet the criteria for a Hy's law case or if any of the individual liver test parameters fulfill any of the SAE criteria.
4. Required at 4 weeks. Then every 3 months thereafter to follow abnormal lab results felt related until resolved to \leq grade 2.
5. It is preferable that both amylase and lipase parameters are assessed. For sites where only 1 of these parameters is routinely measured then either lipase or amylase is acceptable as long as the same one is followed throughout.
6. At least three previous PSA values with the interval between of ≥ 4 weeks, should be recorded for the patient to estimate doubling time as well as one prior to registration.
7. PSA should also be done at the end of the last cycle.
8. All patients at 4 weeks. For patients without PSA progression, repeat every 4 to 8 weeks until progression or until new systemic therapy is initiated.
9. Free T3 and free T4 will be measured if TSH is abnormal.
10. Patients with CR/iCR or PR/iPR or equivocal PD (pseudoprogression)/iUPD should have scans repeated after 4 weeks, but no more than 8 weeks, to confirm response.

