8.0 CRITERIA FOR MEASUREMENT OF STUDY ENDPOINTS

8.1 Definitions

8.1.1 Evaluable for adverse events. All patients will be evaluable for adverse event evaluation from the time of their first treatment.

8.1.2 Evaluable for response. All patients who have received at least one cycle of therapy and have their disease re-evaluated will be considered evaluable for response. Patients who exhibit objective disease progression prior to the end of cycle 1 are considered to be evaluable). Patients on therapy for at least this period and who meet the other listed criteria will have their response classified according to the definitions set out below *[Seymour 2017]*.

Response and progression will be evaluated in this study using the revised international criteria (1.1) proposed by the RECIST (Response Evaluation Criteria in Solid Tumours) committee *[Eisenhauer 2009]* as well as the modified iRECIST guidelines *[Seymour 2017]*. Investigators should note the different requirements for confirmatory scans as well as follow up for the two criteria.

See Section 10 for criteria for continuing treatment past RECIST 1.1 disease progression.

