Complete Response (CR): disappearance of *target* and *non-target* lesions and normalization of tumour markers. Pathological lymph nodes must have short axis measures < 10 mm (Note: continue to record the measurement even if < 10 mm and considered CR). Residual lesions (other than nodes < 10 mm) thought to be non-malignant should be further investigated (by cytology specialized imaging or other techniques as appropriate for individual cases [Eisenhauer 2009]) before CR can be accepted. Confirmation of response is required in this small randomized control trial.

Partial Response (PR): at least a 30% decrease in the sum of measures (longest diameter for tumour lesions and short axis measure for nodes) of target lesions, taking as reference the baseline sum of diameters. Non target lesions must be non-PD. Confirmation of response is required in this small randomized control trial.

Stable Disease (SD): Neither sufficient shrinkage to qualify for PR nor sufficient increase to qualify for PD taking as reference the smallest sum of diameters on study.

Progressive Disease (PD): at least a 20% increase in the sum of diameters of measured lesions taking as references the smallest sum of diameters recorded on study (including baseline) AND an absolute increase of $\geq 5\text{mm}$. Appearance of new lesions will also constitute progressive disease (including lesions in previously unassessed areas). In exceptional circumstances, unequivocal progression of non-target disease may be accepted as evidence of disease progression, where the overall tumour burden appears to have increased by at least 73% in volume or, in select instances where tumour burden has increased sufficiently to require urgent medical intervention (e.g. radiation for spinal cord compression or drainage of a fluid collection. Modest increases in the size of one or more non-target lesions are NOT considered unequivocal progression. If the evidence of PD is equivocal (target or non-target), treatment may continue until the next assessment, but if confirmed, the earlier date must be used.

Patients that are clinically well may continue on therapy following RECIST progression with new lesions or increase in target lesions if the increase in disease burden does not meet the definition of PD by immune response criteria [Seymour 2017]. In this situation, patients do not have unequivocal progression until immune response criteria are met (see Table 2 below).

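### Table 3 scores any patient with iUPD at the first two assessments as iCPD, against 8.3.1 and Table 2, so the primary iRECIST response rate can lose responders; separately, confirmation of iRECIST responses needs one stated rule

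*Combined protocol and SAP*

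**What the plan says.** **Endpoint.** Section 13.2 makes the objective response rate by iRECIST, as defined in Section 8, the primary endpoint, with the RECIST 1.1 rate also reported. Section 13.3 applies a two-stage rule to each arm: at least 1 response in 12 to continue, and at least 4 in 37 for the arm to be considered for phase III.

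**Rule in the text.** Section 8.3.1 requires further progression since the last assessment before iCPD is assigned. On earlier unconfirmed progression it says "As can be seen in Table 3, the prior documentation of iUPD does not preclude assigning iCR, iPR, or iSD" at later time points "or as best overall response (BOR) providing that iCPD is not documented". Table 2 agrees. For progression in target lesions after an earlier iUPD, its entry is "Remains iUPD unless iCPD confirmed based on further increase in sum of at least 5 mm, otherwise remains iUPD", and unchanged new lesions also leave the patient at iUPD.

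**Rule in the table.** Table 3 is introduced with "All patients will have their iBOR from the start of study treatment until the end of treatment classified as outlined below". One row reads iUPD, iUPD, then Anything at every later time point, giving iCPD. The next row reads iUPD, iUPD, iCPD, then Anything, also giving iCPD.

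**Confirmation of response.**
- Note 1 to Table 3: "Table assumes a randomized study where confirmation of CR or PR is not required".
- Section 8.2.5, under the RECIST 1.1 heading: "Confirmation of response is required in this small randomized control trial".
- Section 5.0, footnote 10, on a group that includes iCR and iPR: such patients "should have scans repeated after 4 weeks, but no more than 8 weeks, to confirm response".
- Section 8.1.2: "Investigators should note the different requirements for confirmatory scans as well as follow up for the two criteria".

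**The concern.** Section 8.3.1 cites Table 3 as its illustration, and this row of the table shows the reverse. Two people scoring the same scans, one from the text and one from the table, could count different responders for the primary endpoint.

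The sequence can arise. Section 10.1 keeps clinically stable patients with iUPD on treatment to the next assessment and encourages continuation where pseudoprogression is suspected. A late response after two unconfirmed progressions is what iRECIST is meant to capture. The cut-offs are low, so one reclassified patient can move an arm across a boundary.

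The confirmation question concerns the same endpoint from the other side. If a single unconfirmed PR counts as iPR, the observed rate can be higher than under a confirmed rule, and Section 13.2 does not say which is meant.

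**Working it through.** **1. The passages side by side, for iUPD, iUPD (no worsening), PR, PR**

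| Source | Second assessment | Best overall response |
|---|---|---|
| 8.3.1 | iUPD, no further progression | iPR, since iCPD was not documented |
| Table 2 | remains iUPD | (time points only) |
| Table 3, printed row | iUPD | iCPD |

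The row after the disputed one (iUPD, iUPD, iCPD) would be redundant if the disputed row were intended. That points to a drafting slip. The table reached this review as extracted text with seven cells per body row under six headings. The cell order in this row looks intact and matches its neighbours, but the source table should be checked first.

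**2. The design figures**

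Inputs (13.3): p0 = 5%, p1 = 20%, alpha and beta 0.1, n1 = 12 (continue if X1 ≥ 1), n = 37 (positive if the total is ≥ 4).

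P(positive) = Σ over x ≥ 1 of P(X1 = x) × P(X2 ≥ 4 − x), with X1 ~ Bin(12, p) and X2 ~ Bin(25, p).

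- p = 0.20, for x = 1, 2, 3 and ≥ 4: 0.1859 + 0.2757 + 0.2353 + 0.2054 = 0.902 (power).
- p = 0.05: 0.0434 + 0.0353 + 0.0125 + 0.0022 = 0.093 (alpha).

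A grid search returns 12/37 with these cut-offs as the Simon optimal design, so the plan's figures reproduce.

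**3. Effect of the Table 3 row (losses only)**

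Let f be the share of true responders who have iUPD at both of the first two assessments and are scored iCPD. The documents give no value for f. Then p = 0.20 × (1 − f).

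| f (assumed) | p | Power |
|---|---|---|
| 0% | 0.20 | 90.2% |
| 5% | 0.19 | 88.2% |
| 10% | 0.18 | 85.7% |
| 15% | 0.17 | 82.7% |
| 20% | 0.16 | 79.2% |

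Sensitivity to one lost response at a true rate of 20%:
- P(X1 = 1) = 12 × 0.2 × 0.8^11 = 20.6%. Losing that response stops the arm.
- Of these arms, P(X2 ≥ 3 of 25) = 0.902 would otherwise have ended positive: 0.2062 × 0.9018 = 18.6% of all arms.
- P(X1 ≥ 1 and total = 4) = 5.4%. Losing one response makes the arm negative. This overlaps the previous case, so the two are not to be added.

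These margins describe how the design reacts to any single lost responder. They are not the chance that the defect occurs.

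**4. Effect of accepting unconfirmed responses (second point only)**

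If the null rate is inflated by a share g (assumed), p = 0.05 × (1 + g).

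| g (assumed) | p | Alpha |
|---|---|---|
| 0% | 0.0500 | 9.3% |
| 5% | 0.0525 | 10.7% |
| 10% | 0.0550 | 12.1% |
| 15% | 0.0575 | 13.6% |
| 20% | 0.0600 | 15.1% |

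**The case against.** **Scorers would see the slip.** Table 3 has no row with PR or SD at the first assessment, so it cannot be applied alone. Section 8.3.1 states the rule, the table only illustrates it, and Section 8.3 names the published guideline as its source. This makes literal use of the row less likely. It does not remove the conflict, because the table's lead-in applies it to all patients. Central data review (11.1) verifies endpoints but does not say which text prevails. The RECIST 1.1 rate is little protection, since iUPD starts from RECIST 1.1 progression.

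**A reader might infer that any two consecutive iUPDs are caught.** The row covers only the first and second assessments. SD followed by two iUPDs falls outside it.

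**A reader might infer that giving 8.3.1 precedence settles the matter.** It would not. Its proviso about iCPD has no time limit, while the first five rows of Table 3 keep iCR, iPR or iSD when iCPD comes later. Read literally, 8.3.1 would strip the response from a patient with earlier iUPD who responds and then progresses.

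**A reader might infer that one patient settles an arm's fate.** Section 13.3 is softer: after no responses in stage 1, or fewer than 4 at the end, expansion in PD-L1-positive patients is to be considered, and 4 or more leads only to consideration for phase III.

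**On confirmation, the documents may lean one way.** Section 8.2.5 speaks of this trial as a whole, footnote 10 names iCR and iPR, and Section 8.3 promises the key differences from RECIST 1.1 without listing one on confirming responses. On that view note 1 merely needs aligning. But 8.2.5 sits under RECIST 1.1, 8.1.2 says the confirmatory-scan requirements differ, and Table 3 gives iPR after one PR followed by SD. Neither reading is established.

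**Conclusion.** The Table 3 row is wrong as written, with high confidence, subject to a check of the source table. It contradicts 8.3.1 and Table 2 and bears on how the primary endpoint is scored. Its effect runs one way: it can lower the response rate and power but cannot inflate alpha. The size depends on an unknown share of responders; at an assumed 5% to 20%, power falls from 90.2% to between 88.2% and 79.2%.

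The confirmation point is real but less certain. The rise in alpha from 9.3% to between 10.7% and 15.1%, at an assumed inflation of the null rate of 5% to 20%, belongs to this point alone. The two effects oppose each other, but nothing in the documents shows that they cancel, and the net direction is unknown. The sample size needs no change. The correction should be made before responses are scored.

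**What to change.** **Table 3 (after checking the source table).** Replace the row iUPD, iUPD, Anything with:
- iUPD, iCPD, Anything: iCPD.
- iUPD, iUPD, then CR, PR or SD before any iCPD: iCR, iPR or iSD.
- iUPD, iUPD, then only iUPD or NE, followed by iCPD: iCPD.
- iUPD, iUPD, then only iUPD or NE: iUPD.

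The existing row iUPD, iUPD, iCPD agrees with these.

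**Governing sentence.** State: *iBOR is iCPD if, and only if, iCPD is documented before any CR, PR or SD; iCPD after a response or stable disease does not remove it.* Put the same time limit into the 8.3.1 sentence, so that text and table agree without a precedence clause.

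**Confirmation.** In 8.3 and 13.2, state one rule for the primary iRECIST response rate before scoring. Align note 1 and the rows that depend on it, and report the other version as a sensitivity analysis.

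**Cost.** Wording only. Footnote 10 already asks for repeat scans at 4 to 8 weeks, so no visits, scans or patients are added. The sensitivity analysis rescores the same data.
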